12.2.2.5 Time to Treatment Failure

Time to treatment failure (TTF) is defined as the time from enrollment to discontinuation of treatment for any reason, including disease progression, treatment toxicity, and death.

12.3 Response Review

Responses will be reviewed by the investigator (PI or co-investigator) who is treating the patient at each participating site.

13.0 RECORDS TO BE KEPT / REGULATORY CONSIDERATIONS

Adverse event lists, guidelines, and instructions for AE reporting can be found in Section 8.0 (Adverse Events: List and Reporting Requirements).

13.1 Data Reporting

The Advarra EDC™ and OnCore™ databases will be utilized, as required by the Case Comprehensive Cancer Center and Cleveland Clinic, to provide data collection for both accrual entry and trial data management. Advarra EDC and OnCore™ are Clinical Trials Management Systems housed on secure servers. Access to data through Advarra EDC and OnCore™ is restricted by user accounts and assigned roles. Once logged into the Advarra EDC or OnCore™ system with a user ID and password, Advarra EDC™ and OnCore™ define roles for each user which limits access to appropriate data. Applications for user accounts can be obtained by contacting the OnCore™ Administrator at [contact] for OnCore™ access, and [contact] for Advarra EDC™ access. Advarra EDC™ is designed with the capability for study setup, activation, tracking, reporting, data monitoring and review, and eligibility verification. When properly utilized, Advarra EDC™ is 21 CFR 11 compliant. This study will utilize electronic Case Report Form completion in the Advarra EDC™ database. A calendar of events and required forms are available in Advarra EDC™.

13.2 Regulatory Considerations

The study will be conducted in compliance with ICH guidelines and with all applicable federal (including 21 CFR parts 56 & 50), state or local laws.

13.2.1 Written Informed consent

Provision of written informed consent must be obtained prior to any study-related procedures. The Principal Investigator will ensure that the subject is given full and adequate oral and written information about the nature, purpose, possible risks and benefits of the study as well as the subject's financial responsibility. Subjects must also be notified that they are free to discontinue from the study at any time. The subject should be given the opportunity to ask questions and allowed time to consider the information provided.

The original, signed written Informed Consent Form must be kept with the Research Chart in conformance with the institution's standard operating procedures. A copy of the signed written Informed Consent Form must be given to the subject.

13.2.2 Subject Data Protection

In accordance with the Health Information Portability and Accountability Act (HIPAA), a subject must sign an authorization to release medical information to the sponsor and/or allow the sponsor, a regulatory authority, or Institutional Review Board access to subject's medical information that includes all hospital records relevant to the study, including subjects' medical history.

In order to insure patient safety, investigators and study personnel must have up-to-the-minute health information for subjects enrolled to this study. Therefore, electronic medical records must be utilized to obtain medical information in a timely manner.

13.2.3 Accessing Electronic Medical Records for Cleveland Clinic Foundation (CCF)

For Cleveland Clinic, the electronic systems utilized will be EPIC, COPATH to locate archived pathology records; and AGFA and/or EasyViz to access radiology imaging results

Access to these systems is required for the life of this research study. Information obtained from electronic systems will be copied into the Taussig Cancer Institute research chart and/or printed (lab results, physician notes, etc.) and stored in the research chart. Research charts are kept secure and destroyed according to CCF policy.

Study data will be obtained by the PI, co-investigators, study coordinator, and/or data manager for this study via password-protected login. All study personnel involved in this research will adhere to the CCF policies regarding confidentiality and PHI.

13.2.4 Accessing Electronic Medical Records for University Hospitals (UH)

The following electronic systems will be used: SORIAN to access scheduling information; UH Physician Portal or UHCARE to access lab results, physician notes and to locate archived medical and pathology records; PACS to access radiological imaging results.

Access to these systems is required for the life of this research study. Information obtained from electronic systems will be copied into the Seidman Cancer Center Clinical Trials Unit research chart and/or printed (lab results, physician notes, etc.) and stored in the research chart. Research charts are kept secure and destroyed according to UH policy.

Study data will be obtained by the PI, co-investigators, study coordinator, and/or data manager for this study via password-protected login. All study personnel

CASE 1415

Protocol Version Date: 07/06/2021

involved in this research will adhere to the UH policies regarding confidentiality and Protected Health Information.

13.2.5 Retention of records

The Principal Investigator of the Case Comprehensive Cancer Center supervises the retention of all documentation of adverse events, case report forms, source documents, records of study drug receipt and dispensation, and all IRB correspondence for as long as needed to comply with national and international regulations and the institution in which the study will be conducted, or for the period specified by the sponsor, whichever is longer. No records will be destroyed until the Principal Investigator confirms destruction is permitted.

13.2.6 Audits and Inspections

Authorized representatives of the sponsor, a regulatory authority, an Independent Ethics Committee (IEC) or an Institutional Review Board (IRB) may visit the Center to perform audits or inspections, including source data verification. The purpose of an audit or inspection is to systematically and independently examine all study-related activities and documents to determine whether these activities were conducted, and data were recorded, analysed, and accurately reported according to the protocol, Good Clinical Practice (GCP), guidelines of the International Conference on Harmonization (ICH), and any applicable regulatory requirements.

13.2.7 Data Safety and Monitoring Plan

This protocol will adhere to the policies of the Case Comprehensive Cancer Center Data and Safety Monitoring Plan in accordance with NCI regulations.

14.0 STATISTICAL CONSIDERATIONS

Please refer section 12.2 for endpoint definitions. The primary objective is to evaluate overall response rate. For this patient population, response of 15% or less is unacceptable and 35% or more is promising. Twenty-eight evaluable patients will be accrued; if 8 or more patients respond, then the regimen will be considered promising. The significance level of this one-sided test is 5%, and the power is 82%.

Other end points analyzed are CR, PFS, OS, DOR, and TTF. ORR and CR will be estimated using exact 95% confidence intervals. PFS and OS will be estimated using the Kaplan-Meier method. DOR and TTF will be estimated using standard descriptive statistics such as median and range, or mean and standard deviation.

McNemar's test will be used to compare incidence of CD30 positivity via IHC with multi- spectral imaging and RT-PCR to see if different methods result in different findings.

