6.7.2 Duration of Follow Up

After completion of the study the subjects will be followed for a total of 3 years. The follow up visits will be done at 6, 12, 24 and 36 months after the last cycle of therapy. If the patient is unable to follow up with the local site in person, virtual visits may be used to capture applicable procedures during long-term follow up only.

The follow up visits should include the following:

- Physical Examination
- Vital signs
- Height and weight
- CBC with differential
- Serum chemistry panel as outlined in section **11.1.2**
- ECOG performance status
- Adverse event evaluation (only the adverse events attributed to the study drug)
- Diagnostic CT neck, chest, abdomen and pelvis scan with IV and PO contrast will be done at 6, 12 and 24 months if no disease progression. Neck CT can be omitted if no involvement at baseline

If a virtual visit is completed in follow up every attempt should be made to complete the required assessments listed above, though if they are not completed it will not be considered a protocol deviation.

Patients who have progressive disease or start a new treatment are not required to come in for clinical follow up. These patients can be contacted over the phone by the study personnel to obtain the following information

- Disease status
- Adverse event evaluation only if patients have residual persistent symptoms related to BV treatment
- Current lymphoma treatment

Patients will be followed for toxicity for 30 days after treatment has been discontinued or until death, whichever occurs first. The clinical course of each event will be followed until resolution, stabilization, or until has been determined that the study treatment or participation is not the cause.

Serious adverse events (SAE) that are still ongoing at the end of the study period will necessitate follow-up to determine the final outcome. Any serious adverse event that occurs after the study period and is considered to be possibly related to the study treatment or study participation will be recorded and reported immediately.

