11.1.6 Cycle #4 and #10 day 15 ± 5 days

- CT neck, chest, abdomen and pelvis with IV and oral contrast. Neck CT can be omitted at the discretion of the investigator if there was no involvement seen at baseline.

11.1.7 The treatment will be continued until disease progression, unacceptable toxicity, stem cell transplantation or at physician discretion. If a patient has completed 17 cycles, the treating physician can determine if to continue or discontinue treatment in event there is no disease progression or unacceptable toxicity. Patients who have completed 17 cycles of treatment can continue on the protocol at the discretion of the treating physician until disease progression or unacceptable toxicity. For patients continuing beyond 17 cycles, CT neck, chest, abdomen and pelvis with IV and oral contrast will be done every 6 months ± 2 weeks as long as they are receiving study treatment. Neck CT can be omitted at the discretion of the investigator if there was no involvement seen at baseline. For treatment schedule please refer to section 11.1.5.

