12.2.2.2 Progression Free Survival

Progression-free survival (PFS) is defined as the time from enrollment into the study to disease progression or death due to any cause. The distribution of PFS will be estimated using the Kaplan-Meier method. Disease progression may be defined as the date of documentation of a new lesion or enlargement of a previous lesion, or the date of the scheduled clinic visit immediately after radiologic assessment has been completed. For a patient who is alive without progression at the end of study follow-up, observation of PFS is censored on the date of last contact.

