12.2.2.4 Duration of Response

Duration of response (DOR) is defined as the time from first documentation of objective tumor response (CR or PR) to the time to tumor progression or death due

to any cause.

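### Duration of response is to be summarised without censoring, although it ends at the same event as PFS, which the plan censors; TTF is exposed only for patients still on treatment, or lost on it, at cut-off

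*Combined protocol and SAP*

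**What the plan says.** Section 14.0 splits the time-to-event endpoints into two groups. For the first, "PFS and OS will be estimated using the Kaplan-Meier method". For the second, "DOR and TTF will be estimated using standard descriptive statistics such as median and range, or mean and standard deviation".

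The definitions are in section 12.2:

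- **PFS (12.2.2.2)** ends at progression or death from any cause. For a patient alive without progression at the end of follow-up, "observation of PFS is censored on the date of last contact".
- **DOR (12.2.2.4)** is the "time from first documentation of objective tumor response (CR or PR) to the time to tumor progression or death" from any cause. No censoring rule is given.
- **TTF (12.2.2.5)** is "defined as the time from enrollment to discontinuation of treatment for any reason". No censoring rule is given.

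Two other sections decide whether durations can be incomplete. Section 6.7.2 limits follow-up: "the subjects will be followed for a total of 3 years", with visits at 6, 12, 24 and 36 months after the last cycle and CT scans only up to 24 months. Section 11.1.7 sets no end to treatment: after 17 cycles patients "can continue on the protocol at the discretion of the treating physician until disease progression or unacceptable toxicity". No data cut-off is stated.

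**The concern.** DOR and PFS stop at the same event. If that event has not been seen, PFS treats the patient as censored. DOR offers two options for the same patient, and neither is valid: count the response as ended at the last observation, or drop the patient. Those affected are the patients with the longest responses, so the error is towards understating DOR.

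DOR is a secondary objective (section 2.2) and the plan's only direct summary of how long responses last. Few responders are expected, so one or two ongoing responses can move the summary. With no rule written down, the handling would be chosen after the data are seen.

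TTF differs. It ends when treatment stops for any reason, so it is complete for everyone who has stopped. It is incomplete only for a patient still on treatment, or lost while on treatment, at cut-off.

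**Working it through.** **The plan's own figures.** Section 14.0 gives numbers only for the ORR test. Exact binomial calculation for 8 or more of 28 gives a one-sided level of 4.86% at a 15% response rate and power of 81.8% at 35%, matching the stated 5% and 82%. Nothing below touches this. Expected responders are 28 × 0.15 = 4.2 and 28 × 0.35 = 9.8.

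**Assumptions.** The documents give no DOR for this population and no cut-off. I assume exponential durations with true median *m*, so the true mean is *m*/ln 2, and independent censoring.

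- *m* = 6 months (true mean 8.7) is an assumption.
- *m* = 13 months (true mean 18.8) is an optimistic case. It is the ALCL figure in section 1.3, and ALCL is excluded here.
- Observation after response is a fixed 36 months, or uniform over 12–48 or 3–36 months.

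**Formulas.**

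- Censored fraction, fixed 36 months: *p* = 2^(−36/*m*). For *m* = 6, 2^(−6) = 1.6%; for *m* = 13, 15%.
- Censored fraction, uniform *a* to *b*: *p* = [*m*/(ln 2 × (*b* − *a*))] × (2^(−*a*/*m*) − 2^(−*b*/*m*)). For *m* = 6 over 3–36: (8.66/33) × (0.707 − 0.016) = 18%.
- Mean with censored times counted as complete: true mean × (1 − *p*). For *m* = 6 over 12–48: 8.66 × (1 − 0.0592) = 8.1.
- Plain median, censored times counted as complete: the *t* at which 2^(−*t*/*m*) × P(censoring time > *t*) = 0.5. It equals *m* if no censoring falls before *m*. For *m* = 6 over 3–36, *t* = 5.35: 0.539 × (30.65/33) = 0.50.
- Completed-only median, fixed 36 months: *m* × log2(2/(1 + *p*)). For *m* = 13: 13 × log2(1.744) = 10.4.

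The remaining cells come from simulation.

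| True median | Observation (months) | Censored | Mean (true) | Plain median | Completed-only median |
|---|---|---|---|---|---|
| 6 | fixed 36 | 1.6% | 8.5 (8.7) | 6.0 | 5.9 |
| 6 | 12–48 | 6% | 8.1 (8.7) | 6.0 | 5.5 |
| 6 | 3–36 | 18% | 7.1 (8.7) | 5.4 | 4.6 |
| 13 | fixed 36 | 15% | 16.0 (18.8) | 13.0 | 10.4 |
| 13 | 3–36 | 40% | 11.2 (18.8) | 9.1 | 6.9 |

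**Chance that at least one of 10 responders is censored**, 1 − (1 − *p*)^10. Fixed 36 months: 1 − (63/64)^10 = 15% for *m* = 6, and 80% for *m* = 13. Uniform 3–36: 1 − 0.8186^10 = 86% for *m* = 6, and 99% for *m* = 13.

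**TTF.** Seventeen cycles take 17 × 21 = 357 days, about 11.7 months, and treatment may go on longer. With all patients off treatment there is no bias. With an assumed true median of 3 months and cut-off uniform over 3–36 months after enrollment, 6.6% are censored. The mean is 4.33 × (1 − 0.066) = 4.0 against 4.3, the plain median 3.0 and the completed-only median 2.7.

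**What Kaplan-Meier gives in small samples** (typical estimate over 20,000 samples). With 10 responders, *m* = 13 and 3–36 months, it gives 12.4 against about 9.2 for the plain median. With *m* = 6 and 3–36 months, it gives 5.3 against 5.4 if the median is read as the first time the curve reaches 0.5 or less. If the flat step at 0.5 is averaged, it gives 5.9.

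**The case against.** **The words such as leave room for another method, and the plan is silent on ongoing responders rather than prescribing a biased calculation.** Silence is part of the defect, but not all of it. Section 14.0 sets DOR apart from the endpoints given Kaplan-Meier, names only summaries that assume complete durations, and refers to section 12.2, which has no DOR censoring rule. Carried out as written, it understates the mean whenever a response is ongoing.

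**Thirty-six months is too short for complete follow-up, because it runs from the last cycle while DOR runs from response.** This is partly right. A response found at the cycle 4 scan (about 2.6 months) in a patient completing 17 cycles leaves 11.7 − 2.6 + 36 = 45 months. Censoring is then 0.55% for *m* = 6 or 9.1% for *m* = 13, and the chance that at least one of 10 is censored is 5% or 61%. But scheduled CTs stop 12 months earlier, at 45 − 12 = 33 months for that patient, and patients who stop treatment sooner have less. Thirty-six months is a fair working value.

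**The large effects need early analysis or a borrowed median.** This stands. With *m* = 6 and long follow-up, the plain median is right.

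**Kaplan-Meier is no better with so few responders.** This stands in part. Reading the first time at or below 0.5, *m* = 6 and fixed 36 months, it gives 5.2 against a plain 6.1 at 10 responders and 4.2 against 6.4 at 4. That shortfall comes from the reading convention: averaging the flat step gives about 6.1 at 10 responders. Imprecision remains. With *m* = 13 over 3–36 months the median is not reached in 14% of samples of 4 and 8% of samples of 10.

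**TTF is not at fault.** This is correct once everyone is off treatment. Kaplan-Meier costs nothing there, since without censoring it reduces to the ordinary median.

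**Conclusion.** The concern holds. The method for DOR conflicts with the plan's own treatment of PFS, and the missing censoring rule leaves ongoing responses without valid handling. The mean and the completed-only median are too low whenever any response is ongoing; the plain median over all responders is too low only when censoring comes before it.

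The size depends on how many responses are ongoing, which the documents do not give. Under the assumptions above, the loss in the mean runs from 0.2 months (8.5 against 8.7, 1.6% censored) to 7.6 months (11.2 against 18.8, 40% censored). The upper end combines an early analysis with a median from an excluded population.

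TTF is affected only for patients on treatment, or lost on it, at cut-off. This should be fixed, but it concerns secondary endpoints: the ORR rule, sample size and power do not change.

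**What to change.** In section 14.0, replace the sentence on DOR and TTF with:

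> DOR (responders only) and TTF will be estimated by Kaplan-Meier, reporting the median, its 95% confidence interval and the number censored. Each responder's duration will be listed, with ongoing responses marked.

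In section 12.2.2.4, add:

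> A responder alive without progression is censored by the same rule as for PFS (section 12.2.2.2).

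In section 12.2.2.5, add:

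> Patients still on treatment are censored at the data cut-off; patients lost while on treatment are censored at last contact.

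State the data cut-off and how the median is read when the curve is flat at 0.5. If the PFS censoring date is ever changed, change DOR with it.

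The cost is one replaced sentence, two censoring rules and a stated cut-off, with no new data or visits. With roughly 4 to 10 responders the DOR median will be imprecise, and it or its upper limit may not be reached. The individual listing is there for that reason.

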CASE
COMPREHENSIVE
CANCER CENTER

A Cancer Center Designated by the
National Cancer Institute

Study Number: CASE1415

Study Title: A Phase II Study of Single Agent Brentuximab Vedotin in Relapsed/Refractory CD30 Low (<10%) Mature T-Cell Lymphoma (TCL)

NCT Number: NCT02588651

Principal Investigator: [name], MPH
Cleveland Clinic
[name]
[name]

Ph: [REDACTED]
[REDACTED]

Co-Investigators: [name], PhD
University Hospitals Cleveland Medical Center
[name],
[name]
Ph: [REDACTED]
[REDACTED]

[name]
Karmanos Cancer Institute
[name]
[name]
Telephone: [REDACTED]
[REDACTED]

[name]
[REDACTED]
[REDACTED]

John Theurer Cancer Center at
Hackensack University Medical Center
[name]
[name]

[name]
University of Michigan
Internal Medicine - Hematology/Oncology | North Ingalls
Building
[name]
[name]
[REDACTED]

Cleveland Clinic Sub-Investigators:

[name]
[name]
[name]
[name]
[name]
[name]
[name]
[name]
[name]
[name]

Statistician: [name]
Cleveland Clinic

SPONSOR-Investigator: [name], MPH

Drug Supplier/Supporter: Seattle Genetics

Supplied Agent: Brentuximab Vedotin

IND #: 126990

SCHEMA

Title: A Phase II Study of Single Agent Brentuximab Vedotin in Relapsed/Refractory CD30 Low (<10%) Mature T Cell Lymphoma (TCL)

Objectives:

Primary Objective:

- To determine overall response rate (ORR) of Brentuximab Vedotin in CD30 low (<10%) relapsed or refractory mature T cell lymphoma (TCL)

Secondary Objectives:

- Complete remission (CR) rate
- Duration of response (DOR)
- Progression free survival (PFS)
- Overall survival (OS)
- Time to treatment failure (TTF)

Lab Correlatives:

- To assess and compare the sensitivity of immunohistochemistry (IHC) with imaging analysis and RT PCR methods to detect CD30

Patient Population:

- CD30 low (<10%) relapsed or refractory mature T cell lymphoma (TCL) patients who have received at least one prior therapy.

Study Design:

Phase II study of Brentuximab Vedotin in CD30 low (<10%) mature TCL as determined by current standard IHC.

Inclusion Criteria:

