- Histologically confirmed relapsed/refractory CD30 low (<10%) TCL - including peripheral TCL not otherwise specified (PTCL NOS), angioimmunoblastic T cell lymphoma (AITL), hepato-splenic T cell lymphoma (HTCL), adult T cell leukemia/lymphoma (ATLL), enteropathy associated T cell lymphoma (EATL), and NK T cell lymphoma (NK/TCL)
- CD30 level to be determined by IHC using the anti-CD30 BerH2 antibody
- At least 1 prior chemotherapy regimen
- Measurable disease ≥ 1.5 cm seen on CT scan and/or FDG avid disease on PET scan. Splenomegaly measuring >12 cm, if attributed to TCL and/or positive bone marrow involvement with T cell lymphoma are also eligible
- ECOG performance status (PS) of 0-2. ECOG 3 is permitted if the decreased PS is secondary to lymphoma

- Age 18 years and above
- Able to give informed consent
- Adequate organ function
 - Bilirubin $\leq 1.5 \times$ upper limit of normal (ULN), alanine aminotransferase (ALT) and aspartate aminotransferase (AST) $\leq 3 \times$ ULN even in patients with documented hepatic involvement with lymphoma
 - Serum creatinine clearance $\geq 30 \text{ ml/min}$
 - Absolute neutrophil count (ANC) $\geq 1000/\mu\text{L}$ (unless documented bone marrow involvement with lymphoma)
 - Platelet count $\geq 50,000/\mu\text{L}$ (unless documented bone marrow involvement with lymphoma)
- At least 6 weeks from autologous stem cell transplantation
- At least 3 months from allogeneic stem cell transplantation and off immunosuppression and no evidence of graft versus host disease (GVHD)
- Previous treatment with Brentuximab Vedotin (BV) will be allowed if it was done 6 months prior to enrollment and pt was not refractory or had progressive disease (PD) while on BV
- Females of childbearing potential must have a negative serum or urine pregnancy test result within 7 days prior to the first dose of study treatment. Women of child-bearing age must agree to use an effective contraception method during the study and for at least 6 months following the last dose of study drug. Females of non-childbearing potential are those who are postmenopausal greater than 1 year or who have had a bilateral tubal ligation or hysterectomy.
- Males who have partners of childbearing potential must agree to use an effective contraceptive method during the study and for 6 months following the last dose of study drug.

Exclusion Criteria:

- Anaplastic large cell lymphoma (ALCL) both alk positive and negative

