2.2 Secondary Objective(s)

- Complete remission (CR) rate
- Duration of response (DOR)
- Progression free survival (PFS)
- Overall survival (OS)
- Time to treatment failure (TTF)

2.3 Lab Correlatives:

- To assess and compare the sensitivity of immunohistochemistry (IHC) with imaging analysis and reverse transcription polymerase chain reaction (RT-PCR) methods to detect CD30

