3.0 STUDY DESIGN

This is a non-randomized phase II study of single agent Brentuximab Vedotin in CD30 low, <10%, relapsed/refractory T cell lymphoma subjects. All subjects who meet the eligibility criteria described below will be enrolled to participate in the study. Eligibility criteria may not be waived by the investigator.

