10.0 CORRELATIVE STUDIES

The current standard IHC method using the anti-CD30 BerH2 antibody will be utilized to define CD30 positivity. The other lab correlatives used to detect CD30 are imaging analysis and RT-PCR using RNA isolated from formalin fixed paraffin embedded (FFPE) tissue. We propose to correlate the IHC CD30 positivity using the following methods

- Aperio Image Scanner Analysis and ImageScope Software for IHC quantitation
- Quantification of CD30 mRNA expression levels by RT-PCR on FFPE tissue

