10.2.3 Cell lines, FFPE Blocks

- 1) CD30 positive (Karpas 299) and negative cell line (B lymphoma cell line) control
- 2) FFPE blocks or five 10 micron sections (unbaked on charged slides) of CD30 positive/negative (IHC) tissues.

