10.2.4 Experimental Design

- 1) Set up RT-qPCR with CD30 positive and negative control cell lines at first.
- 2) Calibration curve of RT-qPCR with series diluted RNA isolated from CD30 positive and negative control cell lines.
- 3) RT-qPCR for CD30 positive/negative (IHC) tissues
- 4) Testing with RNA isolated from selected FFPE lymphoma cases and data interpretation.

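### The laboratory aim promises a comparison of CD30 sensitivity, but with IHC-low patients only and no reference standard, section 14.0's McNemar test can show only differing positivity; it also names an imaging method section 10 does not use

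*Combined protocol and SAP*

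**What the plan says.** **Aim.** Section 2.3 states the laboratory correlative as "To assess and compare the sensitivity of immunohistochemistry (IHC) with imaging analysis and reverse transcription polymerase chain reaction (RT-PCR) methods to detect CD30". The schema gives the same aim.

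**Analysis.** Section 14.0 applies McNemar's test to "compare incidence of CD30 positivity via IHC with multi- spectral imaging and RT-PCR to see if different methods result in different findings". It gives no sensitivity estimate, no positivity cut-off for any method and no significance level for this test. It does not say which IHC reading enters.

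**Selection.** The schema's inclusion criteria say "CD30 level to be determined by IHC using the anti-CD30 BerH2 antibody", and section 3.0 describes a study of "single agent Brentuximab Vedotin in CD30 low, <10%, relapsed/refractory T cell lymphoma subjects". Section 11.1.2 has the enrolling site perform this stain. Section 10.0 adds: "The current standard IHC method using the anti-CD30 BerH2 antibody will be utilized to define CD30 positivity".

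**Comparators.** Sections 10.0 and 10.1 describe Aperio scanning with ImageScope, applied to CD30-stained slides. Section 10.2 describes RT-qPCR, reported as a delta-Ct expression level. Section 10.3 has sites send unstained sections to Cleveland Clinic after consent; fifteen of them are for confirming the diagnosis and for CD30 IHC.

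**Set-up material.** Section 10.2.3 lists "CD30 positive (Karpas 299) and negative cell line (B lymphoma cell line) control", and section 10.2.4 includes "RT-qPCR for CD30 positive/negative (IHC) tissues".

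**The concern.** In the diagnostic sense, sensitivity is the share of truly positive samples that a method calls positive, so it needs a truth standard outside the methods compared. Here IHC selects the patients, defines positivity and is one of the methods under comparison. McNemar's test compares two paired positivity rates and does not say which of two discordant calls is right. A significant result could therefore be read, under the objective as worded, as showing that IHC is the less sensitive method, when it shows only that the methods differ in tumours that IHC had already read as low.

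Separately, section 14.0 ties the imaging comparison to multi-spectral imaging, while sections 10.0, 10.1 and 10.3 describe only Aperio. Both are current sections, so the operative text does not say consistently which imaging result is analysed.

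**Working it through.** **Plan's own figure.** None is stated for this comparison. The only design figure in section 14.0 is the response-rate rule (at least 8 of 28; 15% against 35%). It reproduces: exact one-sided alpha 0.0486 and power 0.818, against the stated 5% and 82%. Nothing below touches it.

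**Step 1: can sensitivity be recovered?** The cell lines and tissues in sections 10.2.3 and 10.2.4 give RT-qPCR an analytical control. The tissues are themselves classified by IHC, and no sensitivity analysis is attached to them, so they are not an independent standard for patient samples.

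Take assumed data: 28 IHC-negative tumours, 10 of them RT-PCR positive. The exact two-sided McNemar p is 2 × 0.5^10 = 0.002. Two opposite truths fit these data:
- All 10 are true positives and the other 18 true negatives. RT-PCR sensitivity is 10/10 = 100% and IHC sensitivity is 0/10 = 0%.
- All 10 are false positives and no tumour expresses CD30. RT-PCR specificity is 18/28 = 64%, and sensitivity is undefined.

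The p-value is the same in both cases, so it cannot rank sensitivity.

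**Step 2: what if the 10% threshold is used?** The documents give no positivity cut-off. The only numerical threshold applied to patients is the 10% eligibility limit. Suppose positive meant 10% or more on the site's eligibility reading. Nobody who meets the criteria could then be IHC-positive, so the count positive by IHC only (b) is 0. With a = positive by the other method only, the exact two-sided p is 2 × P(Bin(a+b, 0.5) ≤ min(a, b)). Judging at a two-sided 5% level is my assumption.

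| b | a just short | p | a reaching 5% | p |
|---|---|---|---|---|
| 0 | 5 | 0.0625 | 6 | 0.031 |
| 1 | 7 | 0.070 | 8 | 0.039 |
| 2 | 9 | 0.065 | 10 | 0.039 |

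In the b = 0 row the test is only a check that at least 6 patients are positive by the other method. It can favour that method or show nothing. If 28 patients have usable tissue (assumed), 6/28 = 21%, exact 95% CI 8% to 41%. The chance of reaching 6 is 5.5%, 50%, 89% and 99% when the other method calls 10%, 20%, 30% and 40% of IHC-low tumours positive. With all 31 enrolled patients it is 8.3%, 61%, 94% and 99.6%. Reporting the proportion with its interval therefore loses nothing.

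The rows b = 1 and b = 2 apply once IHC-only patients are possible, through a lower cut-off or a separate IHC reading. The test can then go either way, and the built-in tilt is small or absent.

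**Step 3: is 10% the intended cut-off?** Usage is mixed. Section 1.4 speaks of low-CD30 disease as positive, which points to a lower cut-off; section 1.5 calls such disease negative just before calling it low. The 10% cut-off is neither stated nor excluded.

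**The case against.** The strongest reply is that sensitivity is used loosely. The documents never say diagnostic sensitivity and never mention specificity. Section 1.4 asks whether available methods miss cells that carry CD30, and section 14.0 claims only to look for different findings. For that question IHC-low tumours are the right sample, and McNemar's test on paired calls does address it. This stands. A reader might infer that the correlative has no usable purpose or that the test is invalid; the documents do not support that.

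A second reply concerns the empty IHC-only cell. It needs two things the plan does not state: a 10% positivity cut-off, and use of the eligibility reading. Section 10.3 provides fresh sections for CD30 IHC, separate from the site's stain, on which a tumour read below 10% at the site could read higher. This also stands, so a reader should not conclude that the test is one-sided by design. What remains is that section 14.0 does not name the reading. Section 10.3 also mentions this IHC and the Aperio scanner together, so the two may not be separate readings.

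Third, 28 is the number evaluable for response, not a stated correlative sample size, and section 10.2.5 warns of poor RNA in some tissue. The percentages and intervals above are therefore illustrations. The counts in the table do not depend on the total.

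Finally, this is a laboratory correlative on which no decision rests. That limits the weight. It does not reconcile the objective with the analysis, or section 14.0 with section 10.

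**Conclusion.** The concern holds in a limited form. Diagnostic sensitivity cannot be estimated or ranked from these patients, because IHC both selects them and defines positivity and nothing independent stands behind it. Read as extra detection where IHC is low, the aim is answerable, but McNemar's test can show only that positivity rates differ within IHC-low tumours. The p = 0.031 at 6 patients applies only if the 10% threshold is put on the eligibility reading and the test is judged at a two-sided 5% level. It should not be quoted as a property of the plan as written.

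The imaging mismatch needs no assumption: section 14.0 names a method that current section 10 does not describe.

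The weight is low, since the response-rate analysis, eligibility and safety are unaffected. The change is still worth making, because it alters what the correlative can validly conclude at almost no cost.

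**What to change.** In section 14.0:
1. Replace multi-spectral imaging with Aperio image analysis.
2. Make the main result the proportion of IHC-low patients positive by Aperio and by RT-PCR, each with an exact 95% CI, on the patients with usable tissue. This needs a cut-off for each method, set before patient samples are read; the set-up samples in section 10.2.4 could serve for RT-qPCR.
3. If McNemar's test is kept, do not apply it at the 10% cut-off on the eligibility reading. Name the IHC reading used, for example IHC on the sections submitted under section 10.3, read separately from the Aperio quantification.

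In section 2.3 and the schema:

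4. Replace the aim of comparing sensitivity with describing agreement and CD30 detection within IHC-low disease.

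**Cost.** Wording only, with the same slides, assays and patients. The laboratory claim becomes more modest and the intervals will be wide: at an assumed 28 patients, 3 positive gives 2% to 28%, and 6 positive gives 8% to 41%.
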